**Part 2**

Tapentadol Period – until 12 months after Visit VE
(Treatment: Tapentadol PR)

Subjects transferring before Visit F12M from the Tapentadol Period to the Observation Period will continue in the Observation Period starting from the same trial day number.

Vx = visit number x; VE = End of Treatment Visit for the Treatment Period; ET = early termination Visit after stopping investigational medicinal product during the Tapentadol Period; F12M = visit 12 months after Visit VE; F7D = final post treatment visit; OPx = an unscheduled visit in the Observation Period when the subject stops further participation in the trial; Visit OPn = visit at n months in the Observation Period; PR = prolonged release.

Figure 1: Flow diagram of the trial

Table 1: Schedule of events – Treatment Period

Period	Enrollment	Treatment Period			F7D
		V1	V2	V3	
Visit	-14 to 1	1	8 (± 1)	15 (± 1)	
Day (range)					
Obtain informed consent/assent	X				
Record demographic data	X				
Record age	X	X		X	
Record medical history	X				
Record pain history	X				
Record prior medication intake/therapies	X				
Record concomitant medication intake/therapies	X	X	X	X	X
Perform physical examination	X	X		X	X
Record height	X			X	
Record body weight	X	X	X	X	
Record vital signs	X	X	X	X	X
Record 12-lead ECG	X			X	
Take blood for central laboratory	X			X	
Take blood for local laboratory	X				
Perform urine pregnancy test		X		X	
Collect urine/perform dip stick urinalysis (safety laboratory)	X			X	
Perform urine test for drugs of abuse	X				
Evaluate subject suitability for trial participation: Check inclusion/exclusion criteria	X	X			
Diary set up		X			
Dispense diary		X			
Train/instruct subjects, parents, or legal guardian how:					
1. To use the diary to record pain assessments twice daily (VAS and FPS-R) until Visit VE.					
2. To record intake of IMP and rescue medication, including time of administration.		X	X	X	
Check diary compliance			X	X	
Collect diary				X	
Record pain assessment in diary (VAS, FPS-R)		X			
Record "pain right now" in eCRF (VAS, FPS-R)				X	
Complete questionnaires					
- Modified constipation assessment scale	X	X	X		
- Subjective opiate withdrawal scale				X ^a	
- Acceptability and palatability of IMP			X	X	X ^a
Allocate subjects	X				
Collect returned IMP and rescue medication		X	X		
Perform drug accountability		X	X		

Period Visit Day (range)	Enrollment -14 to 1	Treatment Period			F7D
		V1 1	V2 8 (±1)	VE 15 (±1)	
Dispense IMP (the first dose of IMP will be taken during Visit V2, within 24 hours after randomization. Day 1 is the day of first IMP intake)			X	X	X
Dispense rescue medication			X	X	
Discuss IMP titration/dose adjustment			X	X	X
Train/instruct subject, parent(s), guardian(s), or caregiver on IMP/rescue medication use. Exchange instruction sheet if necessary (e.g., due to weight change).			X	X	X
Take blood sample for serum pharmacokinetics			X	X	X
Dispense subject trial card	X				
Assess/record adverse events	X	X	X	X	X
Document changes of each ongoing adverse event					X
Check discontinuation criteria for IMP intake				X	X
Check subject eligibility for the Tapentadol Period or Observation Period and assign subject to Tapentadol Period or Observation Period					X
Instruct the subject, parent(s), legal guardian(s), or caregiver about the Tapentadol and Observation Periods					X
Complete end of trial tasks, e.g., collect subject trial cards (if the subject is discontinuing from the trial)					X

a) Complete once daily until the seventh day after the last intake of IMP. At Visit VE, or earlier if applicable, dispense the questionnaires. At Visit F7D, collect the completed questionnaires.

Non-invasive procedures, e.g., recording of pain assessment, should be performed before invasive procedures.

Demographic data = date of signing the informed consent/assent form, sex, age, and race/ethnicity; Safety laboratory = hematology, clinical chemistry, and urinalysis; Serum pharmacokinetics = serum concentrations of tapentadol and tapentadol-O-glucuronide; Vital signs = respiratory rate, systolic and diastolic blood pressure, and pulse rate.

VE = End of Treatment Visit after stopping IMP during the Treatment Period; Vx = visit number x; F7D = final post treatment visit; F12M = visit 12 months after Visit VE.

CRF = case report form; ECG = electrocardiogram; IMP = investigational medicinal product; FPS-R = Faces Pain Scale-revised; VAS = visual analog scale; PR = prolonged release.

Table 2: Schedule of Events - Observation Period

Period	Observation Period				
	OP3	OP6	OP9	OPx	F12M
Visit	3	6	9	(unscheduled)	12
Month (range: ± 14 days)					
Record concomitant medication intake/therapies	X	X	X	X	X
Perform physical examination				X	X
Record height				X	X
Record body weight				X	X
Record vital signs (respiratory rate, systolic and diastolic blood pressure, and pulse rate)				X	X
Complete modified constipation assessment scale questionnaire				X	X
Take blood for central laboratory (hematology, clinical chemistry)				X	X
Collect urine/perform dip stick urinalysis				X	X
Assess/record adverse events	X	X	X	X	X
Complete end of trial tasks, e.g., collect subject trial cards				X	X

Months are referenced by last intake of IMP in Part 1.

Visit OPx = an unscheduled visit in the Observation Period when the subject stops further participation in the trial; F12M = visit 12 months after Visit VE; Visit OPn = visit at n months in the Observation Period.

IMP = investigational medicinal product.

Table 3: Schedule of Events - Tapentadol Period

Period	Visit	M1	M2	Tapentadol Period												ET	F12 M	F7D
				TP1	TP2	TP3	TP4	TP5	TP6	TP7	TP8	TP9	TP10	TP11	TP12			
Day (range)		7 (±2)	14 (±2)	28 (±5)	56 (±5)	84 (±5)	112 (±5)	140 (±5)	168 (±5)	196 (±5)	224 (±5)	252 (±5)	280 (±5)	308 (±5)	336 (±5)	Early Termination	365 (±14)	
Record concomitant medication intake/therapies	X	X		X	X	X	X	X	X	X	X	X	X	X	X	X	X	X
Perform physical examination																X	X	X
Record height						X			X			X			X	X	X	
Record body weight				X	X	X	X	X	X	X	X	X	X	X	X	X	X	
Record vital signs	X	X		X	X	X	X	X	X	X	X	X	X	X	X	X	X	X
Complete questionnaires																	X	X
- Modified constipation assessment scale																	X	X
- Subjective opiate withdrawal scale																	X	X
Record “pain right now” in eCRF (VAS, FPS-R)	X	X		X	X	X	X	X	X	X	X	X	X	X	X	X	X	
Take blood for central laboratory						X			X			X			X	X	X	
Collect urine/perform dip stick urinalysis (safety laboratory)							X			X			X		X	X	X	
Perform urine pregnancy test							X			X			X		X	X	X	

Period	Tapentadol Period														ET	F12 M	F7D
	M1	M2	TP1	TP2	TP3	TP4	TP5	TP6	TP7	TP8	TP9	TP10	TP11	TP12			
Visit																	
Day (range)	7 (±2)	14 (±2)	28 (±5)	56 (±5)	84 (±5)	112 (±5)	140 (±5)	168 (±5)	196 (±5)	224 (±5)	252 (±5)	280 (±5)	308 (±5)	336 (±5)		Early Termination	
Train/instruct subject how to use diary to record intake of IMP, including time of administration.	X	X	X	X	X	X	X	X	X	X	X	X	X	X		365 (±14)	
Check diary compliance	X	X	X	X	X	X	X	X	X	X	X	X	X	X	X	X	X
Collect diary															X	X	X
Collect returned IMP	X	X	X	X	X	X	X	X	X	X	X	X	X	X	X	X	X
Perform drug accountability	X	X	X	X	X	X	X	X	X	X	X	X	X	X	X	X	X
Dispense IMP	X	X	X	X	X	X	X	X	X	X	X	X	X	X			
Discuss IMP titration/dose adjustment	X	X	X	X	X	X	X	X	X	X	X	X	X	X			
Train/instruct subject, parent(s), guardian(s), or caregiver on IMP use. Exchange instruction sheet if necessary (e.g., due to weight change)	X	X	X	X	X	X	X	X	X	X	X	X	X	X			
Assess/record adverse events	X	X	X	X	X	X	X	X	X	X	X	X	X	X	X	X	X
Check discontinuation criteria for IMP intake	X	X	X	X	X	X	X	X	X	X	X	X	X	X			
Complete end of trial tasks, e.g., collect subject trial cards																	X

Days are referenced by last intake of IMP in Part 1.

Safety laboratory = hematology, clinical chemistry, and urinalysis; Vital signs = respiratory rate, systolic and diastolic blood pressure, and pulse rate.

Grünenthal
Confidential

Statistical Analysis Plan – KF5503-66
including Amendment 01

Page 14 of 109
DMS version 3.0
13 Feb 2018

VE = End of Treatment Visit after stopping IMP during the Treatment Period; ET = Early termination Visit after stopping IMP during the Tapentadol Period; F12M = visit 12 months after Visit VE; F7D = final post treatment visit; Visit TPx = visit at n months during the Tapentadol Period.
FPS-R = Faces Pain Scale-revised; Modified CAS = modified constipation assessment scale; SOWS = subjective opiate withdrawal scale; VAS = visual analog scale; CRF = case report form; IMP = investigational medicinal product.

5.2 Sample size

The sample size was estimated to reject the null hypothesis of the inferiority of tapentadol PR to morphine PR when comparing responders evaluated at the end of the 14-day Treatment Period (Part 1, i.e., the primary endpoint). The percentage of responders in both treatment arms is estimated to be 80% based on data from previous trials and extrapolation to the trial population under investigation. The non-inferiority margin is set to a difference of 20% for the primary endpoint (i.e., responder rate, see Section 13.1).

To show the non-inferiority of tapentadol PR compared to morphine PR using a Farrington Manning (1990) test by a non-inferiority margin of 20% with at least 80% power and a 1-sided significance level of alpha = 0.1, 69 subjects are required in the FAS, assuming a 2:1 randomization of tapentadol PR:morphine PR.

A one-sided alpha of 0.1 is considered appropriate based on a method proposed by Hlavin et al. (2016). The approach makes use of prior knowledge and the concept of extrapolation from a larger population to a small target population (i.e., pediatric population), to reduce the burden of evidence in pediatrics by relaxing the Type I error, while controlling a certain posterior belief, i.e., confidence after successful pediatric trials, in effectiveness of the drug in children.

Further details for the application of the concept of Hlavin et al. (2016) in the context of this trial are provided in a separate document that is available upon request.

The periodic reviews of the Data Monitoring Committee (DMC) (see Section 6.3) during the trial address only safety and no efficacy data and thus have no impact on the sample size.

5.3 Randomization

Randomization will be done in accordance with the sponsor's standard operating procedures (SOPs).

Randomization will be outsourced to a Central Randomization Center that will develop an Interactive Voice/Web Response System (IVRS/IWRS). The IVRS/IWRS will be used to assign a subject number at the Enrollment Visit as well as a randomization number and medication kit number at randomization.

Eligible subjects will be allocated in the ratio of 2:1 (tapentadol PR:morphine PR) to treatment with tapentadol PR or morphine PR twice daily. A ratio of 2:1 was selected to gain more experience of tapentadol PR in a long-term pain requiring prolonged release opioid treatment setting within a pediatric population.

Stratification by age and underlying pain condition (cancer/non-cancer-related pain) is planned. Stratification by underlying pain condition is foreseen because of the different progression of the underlying diseases and thus different progression of pain scores over time. The predefined age groups are 6 years to less than 12 years, and 12 years to less than 18 years.

6 OVERVIEW OF PLANNED ANALYSES

6.1 Final analyses

Final analysis Part 1

The final analysis of Part 1 will be performed after:

- All subjects have completed Part 1 and the first 12 weeks (Visit TP3 or Visit OP3) of Part 2 of the trial (if not discontinued before),
- And all data of Part 1 and Part 2 up to Visit TP3/OP3 is cleaned.

Together with this final analysis of Part 1, an interim analysis of Part 2 will be conducted. This interim analysis will be based on all data of Part 2 (also including information after TP3/OP3) available in the database at the time point of completion of the cleaning for Part 1 and Part 2 up to Visit TP3/OP3.

For the final analysis of Part 1 and the interim analysis of Part 2, all data available in the database will be fixed in a snapshot. Individual subjects that have completed the entire trial and are clean will be locked.

The final analysis of Part 1 will encompass all analyses of Part 1 as described in this SAP. The interim analysis of Part 2 will encompass all Part 2 analyses planned according to this SAP.

An integrated clinical trial report, integrating clinical, pharmacokinetic, and statistical results of the final analysis of Part 1 and the interim analysis of Part 2 will be prepared by the sponsor.

Final analysis Part 2

The final analysis of Part 2 will be performed once all subjects have completed Part 2 of the trial and the final data base has been hard locked.

The final analysis of Part 2 will encompass all Part 2 analyses as described in this SAP.

A second integrated clinical trial report (optionally as an amendment) will be prepared including the final results of Part 2.

6.2 Interim analyses

As described in the previous section, an interim analysis of Part 2 will be performed.

6.3 Data Monitoring committee analyses

An independent DMC is overseeing and evaluating data from selected pediatric trials with tapentadol administration performed by Grünenthal, including KF5503-66. The purpose of the DMC is to perform an independent and objective review of generated safety data on a regular basis, and to provide recommendations about continuing or terminating the trials or modifying trial protocols or trial conduct. The members of the DMC are independent of Grünenthal and the contract research organization conducting the trial.

Details and operational aspects of the oversight by the DMC were given in a charter. DMS Version 1.0 of this charter was issued on the 06 May 2014 and thus before the first subject-in in this trial.

7 DOCUMENT AND CHANGE HISTORY

7.1 Changes in analysis compared to the trial protocol

Not applicable.

7.2 SAP amendment rationale

7.2.1 Amendment 02

Amendment 02 to the final SAP was prepared to add a few additional analyses and refine some definitions and programming specifications:

1. Additional analyses:

- Analysis for the time to discontinuation from treatment due to “no more need for opioid treatment” during the Tapentadol Period was added, as this is one of the main reasons for discontinuation of treatment of Part 2.
- Summary statistics for the underlying diagnosis/reason for the pain leading to enrollment of the subjects in the trial.
- For all subjects, irrespective of age, one analysis of the primary endpoint based on VAS and one analysis based on FPS-R.
- Subgroup analyses of the primary endpoint for subjects with and without a neuropathic pain component to assess the effect of treatment depending on the type of the underlying pain.
- Overview of the individual response criteria to get a complete picture of reasons for subjects being responder or non-responder.

2. Programming specifications:

- Additional specifications to handle missing data were added:
 - If the time of the first IMP intake is missing, it will be imputed (by 0:00 in case of morning intake or 12:00 in case of evening intake) to derive the time from first IMP intake to first rescue medication intake.
 - In case of a missing intermediate visit during the Tapentadol Period, the visit date will be imputed to derive the average daily dose for the time frame between two scheduled consecutive visits.
 - In case of missing baseline pain intensity for the Tapentadol Period in the eCRF, the last available pain intensity value from the Treatment Period provided in the eDiary will be used as baseline.
 - Missing baseline pain intensities for the Treatment Period will be imputed using the multiple imputation that is used to impute the missing pain intensity values during the last 3 days of treatment.
- Consideration of deviations from the protocol with respect to the time point of visits in relation to IMP intakes:

- Protocol Amendment 02 specifies that subjects should receive their first IMP intake within 24 hours after randomization and that Day 1 is defined as the day of first IMP intake. Therefore, the definition of Day 1 of the trial in the SAP was updated accordingly to ensure clarity and consistency in the specification of Day 1. For the definition of the treatment completers, this redefined Day 1 of the trial will be considered.
- As time to discontinuation refers to discontinuation from *treatment*, it was specified that the dates of first and last IMP intakes should be used for the respective calculations rather than the dates of the scheduled visits.
- The protocol specifies that subjects should have taken their last IMP of the Treatment Period on the day of VE or the evening before. In reality; this intake might have occurred earlier, in particular for subjects that discontinued treatment. For the derivation of the primary endpoint, it was therefore specified that the last 3 days of treatment should be considered for pain assessment rather than the last 3 days prior to VE.
- The options of the multiple imputation were specified more clearly, covering how the imputation by treatment group should be done, which variables to be included in the model and how to handle the different pain scales and the ranges of their respective scores.
- The prior distribution for the precision of the random effects used in the Bayesian analysis of the primary endpoint was redefined based on the expert recommendation provided in the literature (Gelman 2016).
- The factor for the morphine PR equivalent of tapentadol PR that has to be used for some calculations was added.
- A specification of days to be considered for the SOWS (Day 0 = day of last IMP) was added, as deviating from trial day definition.
- For the Z-score related to *weight* and *height*, a rule to derive the age in months based on the available information in years was provided as required for the calculation.

7.2.2 Amendment 01

Amendment 01 to the final SAP was prepared to cover the following topics:

- Changes arising from protocol Amendment 02 dated 23 June 2015 and protocol Amendment 04 dated 23 May 2017 were implemented, including the following major changes:
 - The update of the alpha for the primary endpoint analysis based on the methodology proposed by Hlavin et al. (2016) with the consequence of sample size reduction and use of 80% confidence interval for the primary endpoint analysis.
 - The deletion of the interim analysis for the sample size reassessment due to the sample size reduction. The adaptive 2-stage design of the trial has been simplified to a fixed 1-stage design.
 - The rescheduling of the final analysis of Part 1 such that it will be performed after all subjects have completed the first 12 weeks (Visit TP3 or Visit OP3) of Part 2 and the introduction of an interim analysis of Part 2 at this time point as required by PDCO.
- Further analyses required for public disclosure were added.

- Analyses of the time to trial discontinuation were removed due to the specific trial design. Subjects who discontinue treatment can continue the trial in the Observation Period, which led to a much lower number of trial discontinuations. The time to treatment discontinuation will be investigated.
- Applicable contentwise adaptions according to the actual standard SAP template (SDR-SAP-TRIAL-07) were implemented. Major adaptions are:
 - Type of information to be provided for time to event variables has been updated.
 - Concomitant medication and therapy taken during IMP administration will be flagged and summarized rather than those started after last dose of IMP.
 - Implementation of additional general programming specifications.
 - Use of category “high and low” for laboratory, vital signs and ECG parameters instead of “worst” for overall post-baseline assessment.
- Subgroup analyses prespecified in the previous SAP but not in the protocol were deleted due to the reduced overall sample size.
- Some definitions were further specified to avoid room for interpretation and to cover special cases. Those cover in particular:
 - On-treatment-period for Part 1 and Part 2.
 - Treatment completers and trial completers.
 - Determination of modal dose of IMP.
 - Clearer specification of pain intensity values during the last 3 days of the Treatment Period.
 - Specification of the dose level of IMP during the last 3 days of the Treatment Period.
 - Specification of categories to be used to summarized rescue medication.
 - Specification of the type of graphical displays to be produced for concentration data of tapentadol and tapentadol-O-glucuronide.
 - Specification of “daily average” pain values.
 - Specification of first and last IMP intake.
- Interpretation of the “baseline pain intensity” definition has been broadened based on the change in protocol Amendment 02 that the “first dose of IMP will be taken during Visit V2, within 24 hours after randomization”. Due to this update, the first IMP intake does not necessarily take place on the same calendar day as the randomization (day of V2), but might be the day thereafter. Furthermore, although baseline pain ideally should be assessed before the medication is started, in practice, the first eDiary might be completed only after the first IMP was taken. Therefore:
 1. The last pain intensity value recorded in the eDiary before starting IMP will be considered as baseline pain, which can also be part of an eDiary after the day of V2.
 2. If the first available eDiary entry corresponds to the time point (day and time of the day [morning/evening]) of the first IMP intake, but states that the IMP was already taken, this pain intensity value will nevertheless be used as baseline pain intensity.

The latter is acceptable, as this can be considered as a conservative approach as baseline values will more likely decrease rather than increase after first IMP intake and therefore changes from baseline will more likely become smaller.

- Sensitivity analyses of the primary endpoint were added:
 - Excluding CRPS patients: This additional analysis was planned based on concerns of the DMC chairperson that CRPS patients do not have an appropriate medical indication for inclusion in the trial, as chronic opiate therapy in patients with CRPS is controversial and might be contraindicated.
 - Discarding baseline pain intensity as an explanatory variable in the logistic regression model: As the prerequisites for the measured baseline pain intensity values are highly different between the subjects due to the allowed intake of weak and strong opioid until the day of allocation to IMP (including) and due to the possibility of the first IMP intake before the baseline pain intensity assessment, the robustness of the primary endpoint results without consideration of baseline pain in the model will be evaluated.
 - Adding dose level of IMP during the last 3 days of the Treatment Period as an explanatory variable in the logistic regression model: As a flexible dosing of subjects within different pre-specified weight-depending dose levels is possible, the robustness of the primary endpoint results with consideration of the individual dose level in the model will be evaluated.
- Analysis of exposure adjusted incidence rates was limited to TEAEs of the Tapentadol Period:
 - Due to the short treatment duration of 14-days only and very low rate of discontinuations during the Treatment Period
 - And as AEs assigned to the Observation Period are not considered treatment-emergent. Furthermore, the presentation of confidence intervals for the difference in incidence rates was discarded due to the reduced sample size and the following limited value of information.
- A summary of the height Z-Scores was added to Part 2. Converting heights to Z-score allows for a comparison of heights across ages and sexes and therefore better evaluation over time.
- Description of the multiple imputation approach was improved to provide clearer programming instructions.

Some further minor adaptations (e.g. adding further details or clarifications to individual analyses, rewordings) and minor editorial changes (e.g., the correction of typing errors or format changes) are not specified here.

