8.1.1 Primary endpoint definition

Part 1 (primary analysis of the trial)

The primary endpoint is a binary variable “responder”. A subject is defined as “responder” if both of the following criteria are met:

- Completion of the 14-day Treatment Period (Part 1).
- One of the following calculated from the scheduled pain assessments (“pain right now”) documented during the last 3 days of the Treatment Period:
 - Average pain <50 on a VAS for subjects aged 12 years to less than 18 years; or <5 on the FPS-R for subjects aged 6 years to less than 12 years.
 - Average reduction from baseline of pain ≥20 on a VAS for subjects aged 12 years to less than 18 years; or ≥2 on the FPS-R for subjects aged 6 years to less than 12 years.

The proportion of subjects classified as responders will be assessed and compared between the treatment groups.

Age groups are determined at Visit V2. Baseline pain is defined as “pain right now” at Visit V2, and will be assessed before any painful or unpleasant procedure, and before the first intake of IMP.

Confidential

Protocol KF5503-66
including Amendment 05

Page 39 of 137
DMS version 9.0
27 Jul 2017

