18.1.5.3 Baseline pain intensity of the Treatment Period

According to the protocol, the first dose of IMP should be taken during Visit V2, within 24 hours after randomization. Therefore, the actual day of first IMP intake is not necessarily the same as the day of randomization, but might be the day after the randomization. Based on this, from a programming perspective baseline pain will be derived as follows:

- The pain assessment in the eDiary on the day and at the day time (morning/evening) of the first IMP intake of the Treatment Period will be used as baseline pain.
- In case this eDiary entry is missing, the last available pain assessment before this time point will be used.
- In case this eDiary entry is missing and there is no earlier pain assessment available, baseline pain will be set to missing.

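### SAP 18.1.5.3 can replace a valid pre-dose baseline pain score with one recorded after the first dose

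*SAP*

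**What the plan says.** Protocol 8.1.1 sets baseline pain as current pain at Visit V2, which "will be assessed before any painful or unpleasant procedure, and before the first intake of IMP". SAP 8.2.2 repeats this definition and sends the programmer to SAP 18.1.5.3 for the derivation.

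SAP 18.1.5.3 has three steps. The eDiary assessment "on the day and at the day time (morning/evening) of the first IMP intake of the Treatment Period will be used as baseline pain". Next, "In case this eDiary entry is missing, the last available pain assessment before this time point will be used". If neither exists, baseline is missing. No step asks whether the half-day entry was made before or after the dose.

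SAP 7.2.2, the rationale for Amendment 01, describes a narrower intent. Its first item says: "The last pain intensity value recorded in the eDiary before starting IMP will be considered as baseline pain". Its second item is conditional. It begins "If the first available eDiary entry corresponds to the time point" of the first intake, and covers an entry stating that the dose had already been taken. In that case "this pain intensity value will nevertheless be used as baseline pain intensity". Of this second item the SAP says: "The latter is acceptable, as this can be considered as a conservative approach".

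SAP 7.1 lists no change in analysis from the protocol.

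**The concern.** The programming rule and the definition it is meant to implement part ways in one situation, and the plan allows that situation to arise. The first dose may fall up to 24 hours after randomization, and SAP 18.1.5.3 itself notes that this can be the following day. Protocol 11.1.1.2 has a baseline diary score recorded at V2 before the first intake. For the twice-daily entries, Protocol 12.4.1 makes completion before dosing a preference, not a requirement. A subject can thus record a proper V2 baseline, take the first dose the next morning and fill in that morning's diary afterwards. SAP 18.1.5.3 then takes the post-dose score and ignores the V2 score.

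Baseline enters the primary analysis in three places: the reduction criterion of the responder definition (SAP 13.1), the logistic regression covariate (SAP 13.1.1) and the imputation model (SAP 18.1.8.2). The planned sensitivity analysis that discards baseline pain (SAP 13.1.2, item 4) removes only the covariate. Responder status would still rest on the post-dose score.

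**Working it through.** **1. The rules side by side**

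| Diary situation | SAP 18.1.5.3 uses | SAP 8.2.2 and Protocol 8.1.1 require | SAP 7.2.2 intends |
|---|---|---|---|
| A. Half-day entry made before the dose | that entry | a pre-dose score: met | that entry |
| B. Half-day entry after the dose, nothing earlier | the post-dose entry | a pre-dose score: none exists | the post-dose entry (item 2) |
| C. Half-day entry after the dose, earlier pre-dose entry present | the post-dose entry | the pre-dose entry | the pre-dose entry (item 1) |

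Only case C is an avoidable conflict. It stands on SAP 18.1.5.3 against SAP 8.2.2 and Protocol 8.1.1 alone. SAP 7.2.2 only confirms the intent.

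**2. Who can change status**

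A completer responds if the final average is below 50 (VAS), or if baseline minus final average is at least 20. Anyone below 50 responds whatever the baseline. For the rest, the reduction criterion needs a baseline of at least 50 + 20 = 70. On the FPS-R the figures are 5 + 2 = 7. So if the post-dose score is lower, a change needs completion, a final average of at least 50 (5) and a pre-dose baseline of at least 70 (7).

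Example on the VAS: pre-dose 75, post-dose 60, final average 52. With the pre-dose score, 75 − 52 = 23, so the subject responds. With the post-dose score, 60 − 52 = 8 and 52 is not below 50, so the subject does not.

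At 2:1 allocation, 69 subjects give 46 on tapentadol and 23 on morphine. One changed subject moves the tapentadol rate by 1/46 = 2.2 points or the morphine rate by 1/23 = 4.3 points.

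**3. Illustrative size**

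None of these inputs is in the documents: pre-dose VAS normal with mean 60 and SD 20; fall normal with mean 18 and SD 18; all subjects complete. Simulated responder probability is 0.684 with the pre-dose baseline, 0.637 if the post-dose score is 10 points lower, and 0.621 if it is 20 points lower. If 20% of one arm is affected, that arm's rate falls by 0.20 × (0.684 − 0.637) = 0.9 points or 0.20 × (0.684 − 0.621) = 1.3 points. As a share of that arm's responders, this is 0.20 × 0.047/0.684 = 1.4% or 0.20 × 0.063/0.684 = 1.8%.

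**4. Is a post-dose baseline conservative for non-inferiority?**

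The check uses the unadjusted Farrington-Manning test at 46:23 with margin 0.20 and one-sided alpha 0.1. It first reproduces the plan: exact power at 80% versus 80% is 80.8%, in line with the stated 80% for 69 subjects (the asymptotic formula gives 78.4%). Exact type I error at 60% versus 80% is 10.5%.

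Now suppose a share m of responders loses response because the baseline is lowered, with true rates of 60% and 80%:

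| Loss | Observed rates (tapentadol, morphine) | P(non-inferiority declared) |
|---|---|---|
| none | 60%, 80% | 10.5% |
| m = 5% in both arms | 57%, 76% | 12.2% |
| m = 10% in both arms | 54%, 72% | 14.0% |
| m = 5%, morphine only | 60%, 76% | 18.5% |
| m = 5%, tapentadol only | 57%, 80% | 6.3% |

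A proportional loss shrinks the difference, from 20 points to 19 at m = 5%. An equal absolute loss would leave it unchanged. The table shows direction only: m = 5% is well above the 1.4% to 1.8% in step 3.

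**The case against.** A reader might infer that the SAP calls it conservative to override an earlier pre-dose score. The text does not support that. In SAP 7.2.2 the word applies to the second item only, where the post-dose entry is the first available one. The first item of the same list makes the pre-dose score the baseline, and SAP 18.1.5.3 never uses the word.

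A reader might also infer that post-dose baselines push the trial towards non-inferiority. That is not established. For an individual's reduction, the SAP is right that a lower baseline makes response harder. For the comparison, the direction depends on which arm is affected: loss in tapentadol alone is conservative, while loss in morphine alone is not.

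It is fair to add that an amendment rationale is not the operative text, so a mismatch with it would not be an error by itself. Case C also needs several things together: a first dose in a later half-day than the V2 entry, a diary filled in after that dose, and the score pattern in step 2. Tapentadol PR peaks about 3 to 6 hours after dosing (Protocol 6.2), so an entry made soon after the dose may hardly differ. SAP 13.1.3 summarises each response criterion separately, which will show how far response depends on baseline, though only descriptively. All of this limits the size. None of it removes the conflict between SAP 18.1.5.3 and the definition it implements.

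**Conclusion.** Wrong as written, minor. Where a pre-dose entry exists and the first-dose half-day entry is post-dose, SAP 18.1.5.3 yields a baseline that contradicts SAP 8.2.2 and Protocol 8.1.1. The conflict follows from the text and needs no numerical assumption. The size does: the documents do not say how many subjects are in this situation or how far a post-dose score differs. The estimate of about 1 point in one arm rests on the assumed pain distribution, a 10- to 20-point drop and 20% affected. The error rates in step 4 come from the unadjusted test, not the covariate-adjusted, multiply imputed analysis. The statement that a post-dose baseline is conservative holds for the individual reduction and is not assured for the non-inferiority comparison.

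**What to change.** Reorder SAP 18.1.5.3:

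- Use the last eDiary pain entry made before the first intake. Identify it by the diary's own information on whether the dose had already been taken, or by time where available. Clock time alone is not enough, because SAP 18.1.2.11 allows the first-intake time to be missing. State a default for entries whose order neither source settles.
- Use a post-dose half-day entry only if no pre-dose entry exists.
- Report the number of post-dose baselines by arm.
- Limit the conservative claim in SAP 7.2.2 to the individual reduction.

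An extra run treating the remaining post-dose baselines as missing under SAP 18.1.8.1 is optional. Those subjects could then not respond through the reduction criterion at all, so the run is a bound and not a better estimate.

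The cost is one reordered rule, one default and one count. No new data are needed.
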